## 12. Statistical Design and Methods

### 12.1 Sample size justification

The sample size calculation is based on primary endpoint and it was estimated using data from previous studies with a precision-based calculation. Recent data on post-surgical patient have shown a proportion of patient with the RC markers for the SpO2 ≤ 85% for ≥ 3 minutes at 13% and for RR ≤ 8 or ≥ 22 bpm

for  $\geq 3$  minutes at 1.4% in patients undergoing opioid therapy. Using this information, a minimum proportion of 10% of patients with RC markers with a sample size of 260 patients will be able to obtain a 95% confidence level with a precision of 5% (ranging from 5% to 10%) and a power of at least 0.80 defined as the probability of achieving the desired precision. Considering a 10% withdrawal or potential dropouts and a potential attrition rate to monitoring compliance of 5% a total of approximately 210 patients will be enrolled. This cohort will be used prospectively for the blinded and not blinded phase with a ratio 1:2 respectively to minimize not blinded monitored patients. The blinded phase will enroll 70 patients randomly allocated 1:1 in the Capnostream 20p and PM1000N-RR arm while the not blinded phase will enroll 140 patients with same randomized schedule.

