## 12.3 Analysis of clinical data

Patient demographics and baseline characteristics will be presented using appropriate summary statistics. This includes mean and standard deviation, minimum, maximum and median with the interquartile range [IQR] for continuous variables and counts and percentages for categorical variables. Summary statistics will be reported with maximum 2 decimals, as appropriate. The SAS software (SAS Institute Inc., Cary, NC, USA) will be used to perform statistical analyses. Statistical tests will be based on a two-sided significance level of 0.05. Graphical representations will be used as deemed appropriate. No adjustments for multiple comparisons or multiple look at data will be performed. Outliers and influential observations will be identified via graphical plots and according to study team decision the analysis could be repeated excluding potential outliers. In case of missing data, no imputation method will be implemented for analysis.

The Full Analysis Set (FAS) will be used for primary final analysis. Any patient who does not satisfying the inclusion/exclusion criteria will be eliminate from the FAS population. Details of endpoints analyses and additional analysis will be described in the Statistical Analysis Plan. The analyses of primary objective on the proportion of patient with at least one RC markers will be reported together with their 95% confidence intervals and separately for each arm and phase of the study (see primary endpoint definition). When comparison of clinical primary outcomes is conducted the propensity score methods could be used to control for biases and confounding which may be due to the nature of this study. The

difference between the two groups within phase and between phases within groups will be analyzed by means of unpaired t-test or Mann-Whitney test according to the normal or non-normal distribution. For one secondary outcome the logistic regression model will be used to check potential predictors. Bivariate odds ratios (ORs) and 95% confidence intervals (95% CIs) will be estimated for each predictor. A multivariate logistic regression model will be performed according to univariate model's results. Other secondary outcomes will be performed using sensitivity and specificity analysis.

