## 6. Determination of Sample Size

The sample size calculation is based on primary endpoint and it was estimated using data from previous studies with a precision-based calculation. Recent data on post-surgical patient have shown a proportion of patient with the RC markers for the  $\text{SpO}_2 \leq 85\%$  for  $\geq 3$  minutes at 13% and for  $\text{RR} \leq 8$  or  $\geq 22$  bpm for  $\geq 3$  minutes at 1.4% in patients undergoing opioid therapy. Using this information, a minimum proportion of 10% of patients with RC markers with a sample size of 182 subjects will be able to obtain a 95% confidence level with a precision of 5% (ranging from 5% to 10%) and a power of at least 0.80 defined as the probability of achieving the desired precision. Considering a 10% withdrawal or potential dropouts and a potential attrition rate to monitoring compliance of 5% a total of approximately 210 subjects will be enrolled. This cohort will be used prospectively for the blinded and not blinded phase with a ratio 1:2 respectively to minimize not blinded monitored subjects. The blinded phase will enroll

70 subjects randomly allocated 1:1 in the Capnostream 20p and PM1000N arms while the not blinded phase will enroll 140 subjects with same randomized schedule.

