## 7.9. Evaluation of Objectives

### 7.9.1. Primary Endpoint

The Primary Endpoint of the Study is to quantify the incidence of RC markers in high risk postsurgical patients, using a system comprised of two continuous monitoring devices, connected to a remote monitoring platform. The proportion and rate of “At least one RC marker” event will be calculated and reported.

The “At least one RC marker” event is defined as the occurrence of at least one of the following RC markers:

1.  $\text{SpO}_2 \leq 90\%$  for  $\geq 3$  minutes (or  $\text{SpO}_2 \leq 90\%$  for  $< 3$  min with an action taken);
2.  $\text{RR} \leq 8$  or  $\geq 22$  bpm for  $\geq 3$  minutes (or  $\text{RR} \leq 8$  or  $\geq 22$  bpm for  $< 3$  min with an action taken);
3.  $\text{EtCO}_2 \leq 15$  or  $\geq 60$  mmHg for  $\geq 3$  minutes (or  $\text{EtCO}_2 \leq 15$  or  $\geq 60$  mmHg for  $< 3$  min with an action taken);
4. Apnea episode lasting  $> 30$  seconds.

For patients monitored by PM1000N, only RC markers #1 and #2 will be considered.

RC determination will be assessed by a physician belonging to the “other” site (cross assessment by the sites). This assessment will be made by the analysis of both device and clinical data for each patient. For each patient all potential RC episodes will be derived using the Detection Tool (see Section 10.1) and will be submitted to the other site’s physician in order to adjudicate the potential RC episodes starting from episodes most likely to be RC. The adjudication will stop at the first RC occurring per patient.

The Events’ rates will be computed as (total number of “At least one RC marker” event)/(total number of time-person in PPS) and will be reported separately for each arm and phase of the study. Events’ rates will be displayed together with their 95% confidence interval (95%CI).

If the number of episode per patient result unbalanced, adjusted rates will be reported using the GEE model, together with their 95% confidence interval (95%CI).

If appropriate, also the events’ rates for each RC marker will be reported separately, for each arm and phase of the study.

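### SAP 7.9.1 gives its 95% CI only to person-time rates, in conflict with the protocol's proportion with CI; the 0.80 assurance in SAP 6 belongs to one pooled proportion and to no interval planned by arm and phase

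*SAP*

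**What the plan says.** **Sizing.** SAP section 6 starts from "a minimum proportion of 10% of patients with RC markers with a sample size of 182 subjects", says that this "will be able to obtain a 95% confidence level with a precision of 5% (ranging from 5% to 10%)", and adds "a power of at least 0.80 defined as the probability of achieving the desired precision". It allows for losses ("Considering a 10% withdrawal or potential dropouts and a potential attrition rate to monitoring compliance of 5%") and concludes that "a total of approximately 210 subjects will be enrolled". The 210 are then split into 70 blinded (Phase I) and 140 unblinded (Phase II), each randomised 1:1 between the two monitors. That makes 35 per arm in Phase I and 70 per arm in Phase II.

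**Protocol analysis.** Section 12.3 states that the primary analysis "on the proportion of patient with at least one RC markers will be reported together with their 95% confidence intervals", separately for each arm and phase. The synopsis says the same.

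**SAP analysis.** Section 7.9.1 opens by saying that both the proportion and the rate of patients with at least one marker will be calculated and reported. It then defines the event rate as events over total person-time in the per-protocol set, by arm and phase, and it is these rates that "will be displayed together with their 95% confidence interval (95%CI)". The only other interval in that section, from a GEE model, is also for rates. Adjudication stops at the first RC episode in each patient. SAP 7.3 offers 95% CIs for the primary outcome by centre, as appropriate. No section plans an interval for the pooled cohort.

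**The concern.** The only operating characteristic stated for this pilot is the probability of reaching a given precision on a proportion of patients. A programmer who follows SAP 7.9.1 would report that proportion by arm and phase without an interval and would put the interval on a different quantity. SAP 6 sets no precision target per unit of person-time, so a rate interval cannot be judged against the design target.

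There is a second mismatch. SAP 6 sizes one cohort of 182, while every planned interval is by arm and phase or by centre. A reader of the final report could attach the 5 points and the 0.80 to results from 35 or 70 patients, where they do not hold.

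**Working it through.** **Inputs.** True proportion 10%, two-sided 95% interval, half-width 5 points, assurance 0.80, 182 evaluable and about 210 enrolled (all SAP 6); 35 per arm in Phase I and 70 per arm in Phase II (SAP 6). The stated precision of 5% is taken as a half-width in percentage points.

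**Formula.** Assurance at sample size n is the sum of P(X = x), with X ~ Binomial(n, 0.10), over all counts x whose 95% interval has half-width at most 0.05.

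**1. The plan's own figure.**
- With the Clopper-Pearson interval, the smallest n with assurance of at least 0.80 is 179, within 2% of the printed 182.
- At n = 182 the half-width stays within 5 points for x up to 22, and P(X ≤ 22) = 0.855. With the Wald interval the limit is x = 24, and P(X ≤ 24) = 0.935.
- The inflation also reproduces: 182 × 1.15 = 209.3 and 182 × 1.10 × 1.05 = 210.2.

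So 182 and 210 come from a precision calculation for one pooled binomial proportion. Protocol 12.1 still prints "with a sample size of 260 patients will be able to obtain a 95% confidence level with a precision of 5%" beside a total of 210. Since 260 × 1.15 = 299, that figure fits the superseded total of 300, and the SAP's 182 is used here.

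**2. The same criterion by arm and phase, as Protocol 12.3 plans its intervals.**

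| Patients | Interval | Half-width at 10% (points) | Largest count within 5 points | Assurance |
|---|---|---|---|---|
| 182 (pooled) | Clopper-Pearson | 4.6 | 22 | 0.855 |
| 182 (pooled) | Wald | 4.4 | 24 | 0.935 |
| 70 | Clopper-Pearson | 7.7 | 2 | 0.024 |
| 70 | Wald | 7.0 | 3 | 0.071 |
| 35 | Clopper-Pearson | 11.2 | none | 0.000 |
| 35 | Wald | 9.9 | 0 | 0.025 |

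For n = 35 the expected count is 3.5, and the formulas are evaluated at that value. The last assurance is 0.9^35 = 0.025, the chance of seeing no event at all. These sizes are before losses. Applying 182/210 gives about 61 and 30 evaluable, with Clopper-Pearson half-widths of 8.3 and 12.2 points.

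**3. The rate interval.** Assume one event in each of 7 patients out of 70, an exact Poisson interval, and mean monitoring anywhere between the 24-hour minimum and the 72-hour maximum. The rate is then between 10.0 (4.0 to 20.6) and 3.3 (1.3 to 6.9) per 100 patient-days. The absolute width depends on monitoring time, which the sizing does not use, so neither the 5 points nor the 0.80 carries over.

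**4. Data structure.** Because adjudication stops at the first RC episode, each patient contributes 0 or 1. That is the binomial outcome for which SAP 6 is written.

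**The case against.** **The interval is already planned.** Protocol 12.3 and the synopsis promise it, the SAP says that it is based on that protocol version, and SAP 7.9.1 does report the proportion. This stands. A reader might infer that the sized kind of interval has been dropped from the trial altogether; the documents do not support that. They show the two documents disagreeing about which primary statistic carries a CI. Anyone holding the counts and denominators could also compute a binomial interval, so the information is not lost.

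**The switch to a rate destroys the precision.** A reader might compare 0.855 for the exact binomial interval at n = 182 with 0.543 for an exact Poisson interval on the same events expressed per patient. The documents do not support making this the size of the problem. SAP 7.9.1 names no interval method, the comparison assumes equal monitoring time, and a Wald-type Poisson interval gives 0.796. The drop is largely a threshold effect: at 18 events the half-widths are 4.88 and 4.61 points, a difference of about 0.3 points; at 19 events the Poisson half-width is 5.01 and just fails.

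**The parenthesis in SAP 6 might mean a tolerance of up to 10 points in the smaller groups.** SAP 6 does not say so. Even on that reading, assurance at n = 70 is 0.997 (Clopper-Pearson), but at n = 35 it is only 0.306 (Clopper-Pearson, counts up to 2) to 0.531 (Wald, counts up to 3).

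**This is a descriptive pilot.** That is true: the primary endpoint has no hypothesis test, so no error rate is affected. It limits the weight of the point but does not remove the conflict.

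**Conclusion.** The point holds in two parts. First, SAP 7.9.1 conflicts with Protocol 12.3 and the synopsis: the protocol puts the 95% CI on the proportion, the SAP puts it on person-time rates. Second, the 0.80 holds for one pooled proportion (0.855 with Clopper-Pearson at n = 182) and for no interval planned by arm and phase, where the chance of 5-point precision is 0.024 to 0.071 at n = 70 and 0.025 or less at n = 35. Restoring the protocol's interval therefore settles the conflict but does not deliver the stated precision in any arm and phase.

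This rests on a true proportion of 10%, a 5-point half-width, and full enrolment in each arm and phase; losses make it worse. The pooled figure needs its own caveat, because the endpoint counts four markers on one device and two on the other, so a pooled proportion mixes two definitions. The correction should be made before analysis; it does not call the enrolment target into question.

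**What to change.** - **SAP 7.9.1:** make the proportion of patients with at least one RC marker the primary estimate, with a Clopper-Pearson 95% CI for each arm and phase, as in Protocol 12.3. Label the person-time rate and its CI, crude or GEE-adjusted, as supportive.
- **SAP 6:** state that the 5-point precision and the 0.80 refer only to the binomial interval of the pooled proportion, with the caveat about the two marker sets. Print the expected precision for each arm and phase: at 10%, about 7.7 points for 70 patients and 11.2 points for 35 before losses. Without the word pooled, the sentence would invite readers to attach 0.80 to the individual arms and phases.

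The cost is a few sentences and one standard output table. It needs no new data and no change to enrolment.

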### 7.9.2. Secondary Endpoints

The secondary endpoints are:

1. To compare phases in terms of Primary endpoint incidence;
2. To compare phases in terms of respiratory and SAE incidence, number of ICU transfers and related length of stay, Code blues and RRT responses.
3. To evaluate the rate of clinical early interventions performed by nurse staff to prevent a potential AE, introducing continuous monitoring devices connected to a remote monitoring platform;
4. To evaluate the nurses’ satisfaction related to the monitoring system introducing continuous monitoring devices connected to a remote monitoring platform;
5. To establish the Predictive values of  $\text{EtCO}_2$ , RR,  $\text{SpO}_2$ , plethysmography-derived RR, IPI and EWS in respect to respiratory and other SAE.

In order to evaluate secondary **endpoints #1 and #2**, the incidence of events will be reported together with the comparison between phases, by means of the Chi-square test or Fisher exact test for extreme

proportions, as appropriate. If the monitoring/study exposure results different between phases, also the rates of events will be reported, together with the 95% Poisson Confidence Intervals. The Poisson regression model will be used to calculate the Incidence Rate ratio (IRR), with the d-scale option.

For **endpoint #3**, the rate of clinical early interventions will be calculated as (number of early interventions)/(total time-person in FAS) and it will be reported together with the 95% Poisson Confidence Interval.

Early interventions include, as defined in CRF (Monitoring Period):

1. Stimulated subject to breathe;
2. Repositioned/opened airway;
3. Held or reduced Respiratory Depressive (RD);
4. Added or increased supplemental oxygen;
5. Ventilation support;
6. Other

**Endpoint #4** will be evaluated reporting a summary of the nurses' satisfaction answers.

To identify the predictive values for EtCO2, RR, SpO2, plethysmography-derived RR, IPI and EWS, which can predict respiratory and other SAE, a sensitivity analysis will be performed (**endpoint #5**), and the following parameters will be reported, for each RC marker:

1. **Sensitivity** = 
$$\frac{(\# \text{ of clinical events "Yes" and with RC marker "Yes"})}{(\# \text{ of clinical events "Yes"})} = \frac{TP}{(TP+FN)}$$
2. **PPV** = 
$$\frac{(\# \text{ of clinical events "Yes" and with RC marker "Yes"})}{(\# \text{ of events with RC marker "Yes"})} = \frac{TP}{(TP+FP)}$$

RC marker	Clinical Events		Total
	Yes	No	
Yes	(TP)	(FP)	(TP + FP)
No	(FN)	(TN)	(FN + TN)
Total	(TP + FN)	(FP + TN)	(TP+TN+FP+FN)

To perform this analysis, a temporal window to find RC markers that could be associated with a clinical event will be defined (for example  $\pm 1$  minute from the event).

Due to the impossibility to identify the true negatives (TN), both the specificity and the NPV could not be calculated.

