Early Warning Score	EWS	Physiologic track and trigger systems, based on patients' vital signs, used to monitor adult patients in acute hospital settings to prevent Adverse Events.
Electronic Case Report Forms	eCRF	Forms where the clinical data are collected. eCRF is the electronic version of case report forms.
Ethical Committee	EC	Any board, committee, or other group formally designated by an institution to review, to approve the initiation of, and to conduct periodic review of, biomedical research involving human patients. The primary purpose of such review is to assure the protection of the rights and welfare of the human patients.
End Tidal CO 2	etCO 2	The numeric partial pressure of the maximum value of carbon dioxide in the exhaled breath over the last 20 seconds. The etCO 2 numeric value is updated once a second.
Intensive Care Unit	ICU	Acute care with 24 hour coverage. Patients may be directly transferred from the OR to the ICU or via the PACU.
Integrated Pulmonary Index™	IPI	The Integrated Pulmonary Index (IPI) is a composite index of etCO 2 , SpO 2 , RR and PR that is intended to indicate changes in physiological status as indicated by the monitored variables and cleared by FDA (K082268) in 2009.
Preoperative Score to Predict Postoperative Mortality Score	POSPOM Score	POSPOM Score is an accurate risk score for predicting in-hospital mortality in patients undergoing surgery, calculated based on preoperative data such as on patient's age, planned

Term	Abbreviation	Definition
		surgery and presence of additional diseases or disorders.
Pulse Rate	PR	Pulsatile cycle in beats per minute via pulse oximeter technology.
Pulse Oximetry	SpO 2	Depends on pulsatile blood flow and measures only the oxyhemoglobin in arterial blood as it leaves the heart.
Rapid Response Team	RRT	A team of health care providers that responds to hospitalized patients with early signs of deterioration on non-intensive care units to prevent respiratory or cardiac arrest.
Respiratory Compromise	RC	Respiratory compromise consists of respiratory insufficiency, compromise, distress, arrest, and failure. Respiratory Compromise is a state in which there is a high likelihood of decompensation into respiratory insufficiency, respiratory failure or death, but in which specific interventions (enhanced monitoring and/or therapies) might prevent or mitigate decompensation.

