## 8. Study Procedures

### 8.1 Schedule of Events

Data will be collected for Screening, Enrollment Visit and Monitoring Period. Additional data will be collected for Adverse Events, Device Deficiencies and Protocol Deviations.

Data collection requirements are summarized in Table 2. The study site personnel must report all study specific Adverse Events and changes in status of these Adverse Events from time of enrollment until a patient exits the study.

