## 8.4 Patient Consent

The investigator or authorized designee must obtain written informed consent before any clinical study related activity takes place. Written informed consent must be obtained prior to surgery.

In advance of the consent discussion, the patient should receive the EC approved Patient Information and Informed Consent Form. During the consent discussion, the investigator or his/her authorized designee must fully inform the patient of all aspects of the clinical study that are relevant to the patient's decision to participate in the clinical study. If a patient is illiterate, an impartial witness must be present during the entire informed consent discussion. All items addressed in the Patient Information and the Informed Consent Form must be explained. The language used shall be as non-technical as possible and must be understandable to the patient and the impartial witness, where applicable.

The patient must have ample time and opportunity to read and understand the Patient Information and the Informed Consent Form, to inquire about details of the clinical study, and to decide whether or not to participate in the clinical study. All questions about the clinical study should be answered to the satisfaction of the patient.

Neither the investigator, nor the investigation site staff shall coerce or unduly influence a patient to participate or to continue to participate in the clinical study. The informed consent process shall not waive or appear to waive the patient's rights.

When the patient decides to participate in the clinical study, the Informed Consent Form must be signed and personally dated by the patient and investigator or authorized designee. If applicable, the witness shall also sign and personally date the consent form to attest that the information in the Patient Information and Informed Consent Form was accurately explained and clearly understood by the

patient, and that informed consent was freely given. Detailed documentation of the process must be recorded in the patient's case history.

After all persons have signed and dated the Informed Consent Form, the investigator must provide the patient with a copy of the Patient Information and the Informed Consent Form.

Medtronic will inform the investigators whenever information becomes available that may be relevant to the subject's confirmed participation in the clinical study. The investigator or his/her authorized designee should inform the patient in a timely manner.

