## 8.5 Enrollment

The point of enrollment is completion of informed consent and confirmation of inclusion/exclusion criteria per the screening evaluation.

Data collected for enrolled patients includes:

- Medical history (including surgical, apnea, and medical therapy such as oxygen use and opioid use)
- Demographic & Physical exam
- Vital signs
- Supplemental oxygen use
- Surgery information

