## 8.7 Monitoring Period

Continuous monitoring from either Capnostream™ 20p or Nellcor Monitoring Systems will be performed on all patients for a minimum of 24 hours. The monitoring period will last up to patient's full mobilization or up to a maximum of 72 hours, if the patient is still bed-ridden after two days post-surgery.

The monitoring period will start for patients once they arrive on the ward. For patients who are determined to be at high risk due to opioid therapy and not due to other pre-existing factors, monitoring of capnography and pulse oximeter data will start only after opioid therapy has been initiated.

Monitoring may be discontinued if the patient is discharged from the hospital ward.

During Phase I the alarm feature of the monitoring devices will be silenced and the screen information blinded. A regular check during the monitoring period should be completed to ensure the etCO2 filter line and SpO2 sensors are appropriately fitted on the patient.

During Phase II the medical staff will be instructed to respond to alarm feature of the monitoring devices and their screen will be open. A guideline will be created to instruct the nurses in responding to alarms and changes in the monitored parameters. An alarm will be considered a false positive by the observer if the SpO2 sensor or the etCO2 filter line is off the patient or misplaced. Alarms will be considered true positive if the SpO2 sensor and etCO2 filter line placement is correct: observations on patient activity and subsequent interventions will be recorded in the eCRF to identify clinically significant or insignificant alarmed events. As an example, patient activities such as talking, eating or gripping a book with the SpO2 sensor compressed will be marked as true positive with details of the activity recorded to identify the alarmed event as potentially clinically insignificant if no medical intervention was taken. The Monitoring eCRF will be completed to document:

- Care pathway (location/transfer within hospital)
- Alarm threshold applied to the monitor (to be collected during the Monitoring Phase II only for each measured parameter, PR, RR, SpO2 and EtO2).
- Systolic blood pressure and level of consciousness using the AVPU scale to allow the retrospective NEWS analysis
- Monitoring duration
- Vital signs
- Supplemental oxygen use
- Medications
- Product information

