**Table 5. Anticipated Respiratory Adverse Events**

Partial airway obstruction that required an NMBA antagonist
Respiratory Insufficiency that would require Non-invasive positive pressure ventilation, ambu bag mask assisted ventilation
Respiratory failure that would require Invasive mechanical ventilation
Upper airway obstruction requiring airway support measures (oral or nasal) such as intubation or Laryngeal Mask Airway
Respiratory insufficiency/failure that would require a transfer to the ICU
Cardiopulmonary arrest
Death due to respiratory/pulmonary related complications

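### Secondary endpoint #2 has no at-risk window: AEs and SAEs that begin before ward monitoring are counted to a phase, and the window for ICU transfers, Code blues and RRT responses is undefined

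*SAP*

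**What the plan says.** - **The endpoint.** SAP 7.9.2 gives endpoint #2 as "To compare phases in terms of respiratory and SAE incidence, number of ICU transfers and related length of stay, Code blues and RRT responses". Phases are compared by chi-square or Fisher test. If exposure differs, rates and a Poisson incidence rate ratio are added. No onset rule is given.
- **The denominator.** SAP 7.9.2 names monitoring or study exposure without choosing. Under SAP 7.7, study exposure runs from enrolment and monitoring exposure from the start of monitoring.
- **The analysis sets.** SAP 7.1.3 assigns endpoint #2 to both FAS and PPS. Both require that the patient was monitored.
- **AE reporting.** Protocol 8.1 requires sites to report "Adverse Events from time of enrollment until a patient exits the study". Protocol Table 2 and SAP Table 1 both mark adverse events at Enrollment. Protocol 8.8 puts study exit at hospital discharge and makes events after the end of monitoring reportable.
- **Enrolment.** Protocol 8.5: "The point of enrollment is completion of informed consent and confirmation of inclusion/exclusion criteria per the screening evaluation". Protocol 8.4: "Written informed consent must be obtained prior to surgery".
- **Start of monitoring.** Protocol 8.7: "The monitoring period will start for patients once they arrive on the ward". It starts later for patients whose high risk comes only from opioid therapy.

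**The concern.** The phases differ in whether alarms and screens are active, and that applies only while a patient is monitored. An event that begins earlier cannot be influenced by it. Endpoint #2 is where the plan compares the phases on clinical outcomes, so what enters its numerator matters.

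Two things can go wrong. If pre-monitoring events are equally common in both phases, they add the same background to each side and the ratio moves toward 1. If they are not equally common, the difference appears as an effect of monitoring. Patients are randomised to device within phase, not to phase, and the phases run one after the other with at least a month between, so nothing in the design balances what happens before the ward.

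**Working it through.** **Passages side by side**

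1. AE/SAE reporting opens at enrolment (Protocol 8.1).
2. Enrolment is consent plus confirmed criteria (8.5). Consent precedes surgery (8.4). POSPOM uses planned surgery (7.3, Appendix E), so a POSPOM-eligible patient can be enrolled before theatre.
3. Monitoring starts on ward arrival or later (8.7).
4. There is therefore an interval in which an AE or SAE is reportable but the patient is not monitored. Requiring monitoring for the FAS removes patients who never reach it; it does not remove earlier events in those who do.
5. SAP 7.9.2 and 7.10 contain no filter. By contrast, SAP 7.9.2 ties the interventions of endpoint #3 to the monitoring-period form.
6. For ICU transfers, Code blues and RRT responses there is no counting rule in either direction.

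**The plan's own figure.** The documents give no power, effect size or event rate for endpoint #2. The only calculation, 182 inflated to about 210 (SAP Section 6), is for the precision of the primary endpoint. It reproduces: an exact Clopper-Pearson search gives 179, and 182 × 1.15 = 209.3. It does not bear on this point.

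**Inputs.** From the documents: 70 and 140 patients, two-sided 0.05. Assumed: ward risk p from the start of monitoring, pre-monitoring risk q, and independence of the two.

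**Formula.** Observed risk = 1 − (1 − q)(1 − p). For q = 10%: Phase I, 1 − 0.90 × 0.80 = 0.28; Phase II, 1 − 0.90 × 0.90 = 0.19; ratio 0.19/0.28 = 0.68. Power is the exact binomial probability that the uncorrected chi-square test rejects.

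Ward risk 20% v 10%, same q in both phases:

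| q | Phase I | Phase II | Difference (points) | Ratio | Power |
|---|---|---|---|---|---|
| 0 | 20.0% | 10.0% | 10.0 | 0.50 | 0.51 |
| 2% | 21.6% | 11.8% | 9.8 | 0.55 | 0.46 |
| 5% | 24.0% | 14.5% | 9.5 | 0.60 | 0.40 |
| 10% | 28.0% | 19.0% | 9.0 | 0.68 | 0.33 |
| 20% | 36.0% | 28.0% | 8.0 | 0.78 | 0.22 |

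With ward risk 10% v 5%, q of 2%, 5%, 10% and 15% moves the ratio from 0.50 to 0.58, 0.67, 0.76 and 0.82. Power (normal approximation) falls from 0.30 to 0.24, 0.19, 0.14 and 0.11.

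**Rate ratio.** Suppose monitoring time is equal and expected ward events per patient are 0.10 v 0.05. Adding q to each numerator gives (0.05 + q)/(0.10 + q): 0.58, 0.67 and 0.75 for q = 0.02, 0.05 and 0.10.

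**Unequal q, no ward effect (15% in both phases).**
- q of 20% v 10%: 1 − 0.80 × 0.85 = 0.320 and 1 − 0.90 × 0.85 = 0.235. The ratio is 0.73, and the test rejects 27% of the time.
- q of 2% v 1%: 16.7% v 15.85%. The ratio is 0.95, and the test rejects 5.4% of the time, close to nominal.

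**The case against.** **Enrolment may follow surgery.** Inclusion criterion 1 describes a post-surgical patient. Eligibility can still fail up to ward monitoring (Protocol 8.2). Surgery details and drugs used in theatre and recovery are collected at enrolment (8.3, 8.5), and ARISCAT scores the duration of surgery (Appendix E). If enrolment is confirmed after surgery, theatre events and many recovery events fall outside the AE window. This stands: the documents leave the timing open. It does not close the gap, because a direct ICU stay, or ward time before an opioid-linked start, can still lie between enrolment and monitoring.

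**Stronger readings the text does not support.** A reader might infer that ICU transfers are counted from enrolment, so that a planned direct post-operative ICU stay scores as a transfer. The glossary does say "Patients may be directly transferred from the OR to the ICU or via the PACU", but it describes routes into an ICU and does not define the endpoint. The enrolment-to-exit rule covers adverse events only, and location and transfer are recorded on the Monitoring eCRF (8.7). A reader might also take "Partial airway obstruction that required an NMBA antagonist" in Appendix A, Table 5 as a sign that theatre or recovery events are meant to count. The appendix introduces the table as events in high-risk post-surgical patients and gives no place or time.

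**The size is assumed.** This also stands. At 2% to 5% pre-monitoring risk the loss is modest, and the risk difference barely moves. This is a pilot with no stated power for endpoint #2.

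**An onset filter does not remove confounding.** Also correct: changes in practice between sequential phases affect ward events too.

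**Conclusion.** The concern holds as an undefined window. For AEs and SAEs, following the plan as written counts events with onset after enrolment but before monitoring, in patients later monitored, to a phase that could not have affected them. For ICU transfers, Code blues and RRT responses the plan gives no window and does not say whether a direct ICU stay from theatre or recovery counts, so two programmers could reach different totals. It would go too far to say that the plan directs ICU transfers to be counted from enrolment, or that enrolment always precedes surgery.

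The direction is clear. With equal pre-monitoring risk, a true ratio of 0.50 is pulled toward 1; with unequal risk, a spurious difference can appear. The size cannot be derived from the documents: it runs from small at a pre-monitoring risk of 2% (power 0.46 instead of 0.51) to large at 20% (0.22), under the assumed ward risks and independence. The same gap exists at the other end, since events from the end of monitoring to discharge are reportable with no rule for endpoint #2. Because the remedy needs little, the SAP should make it.

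**What to change.** In SAP 7.9.2, for the phase comparison on endpoint #2:

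1. Count only events with onset at or after the recorded start of monitoring and up to one stated end: end of monitoring as the main window, hospital discharge as a supportive one. AE date and time are already required (Protocol 10.2), and SAP 7.7 already uses the date and time of monitoring start and end.
2. Use the matching person-time for rates and the incidence rate ratio, in place of the open choice between monitoring and study exposure.
3. Count ICU transfers only when they are from the ward after monitoring has started, with ICU stay measured from that transfer. Apply the same window to Code blues and RRT responses.
4. Tabulate earlier events and direct post-operative ICU stays separately by phase, so that any imbalance is visible.
5. Keep the full AE window in the SAP 7.10 safety tables and listings.

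The cost is SAP wording and a date/time filter. Location and transfer are already on the Monitoring eCRF, but the documents do not say that transfers, Code blues and RRT responses carry a time, or that transfers are captured after monitoring ends; this should be confirmed. A planned/unplanned restriction is not proposed, because no such field is shown to be collected. The downside is fewer counted events, and confounding between the sequential phases in ward events remains.
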